13 DOCUMENTATION OF TRIAL DATA

13.1 Case report forms

Case report forms for each subject will be provided to the investigator by the sponsor in electronic format to document the trial data.

The investigator will use CRFs to record information required by the protocol to be reported on each trial subject. The investigator will be instructed on how to complete the CRFs.

The investigator will verify that the CRFs are complete, accurate, and compatible with source documents. All CRF entries, corrections, and alterations will be made by the investigator or other authorized personnel under their supervision. Entries will be checked against appropriate source documents by the sponsor's representative (e.g., clinical research associate).

Electronic case report forms

The data will be processed using a validated system. Access to the system will be protected with a personal user name and password. The users are identified and receive access rights according to their role in the trial. All users will receive training on the CRF, and this training will be documented prior to access rights being granted.

The investigator, the clinical research associate, and designated persons at the trial site and from other parties involved (e.g., data management staff) will have access to review all captured data during the trial via a secure internet connection.

After source data verification, the applicable part of the CRF will be flagged as source data verified. Should subsequent changes be made, this flag will be reversed and source data verification must be repeated.

All entries and modifications to the CRF will be stored with the personal identification of the person who made the changes, a date/time stamp, and the reason for change.

The CRF must be signed electronically by the investigator. Any changes made to the CRF pages after the investigator has signed will require a re-signing by the investigator.

13.2 Subject reported outcomes

Diaries for each subject will be provided to the investigator by the sponsor in electronic format for Treatment Period of Part 1 to document the pain assessments (VAS and FPS-R) and intake of IMP and rescue medication, and for Tapentadol Period of Part 2 to document the intake of IMP. The other questionnaires will be reported on paper throughout the trial. An electronic version of the VAS will be used in the electronic diary (Part 1) and paper version of the VAS will be used in the CRF for the Tapentadol Period (Part 2). The electronic version and the paper version of the VAS are both validated.

Subjects will receive their diaries at the investigator's site and will be instructed on how to use it.

Due to the fact that this is a pediatric trial, the possibility for caregivers to enter data in the diaries is possible and will be recorded with a personal identification of the person who made the entry.

Confidential

Protocol KF5503-66
including Amendment 05Page 85 of 137
DMS version 9.0
27 Jul 2017

The data will be collected using an appropriately validated system. No queries will be issued to the investigator for these data, except for clarification of subject identifiers and any operational issues.

13.3 Data management

Data management will be performed by sponsor personnel or by authorized sponsor representatives defined by the sponsor prior to the trial start.

Electronic case report forms

During data entry in the electronic CRF, automatic queries will be raised to clarify missing data, inconsistencies, and incorrect values. After completion of the CRF, further queries will be issued to the investigator to clarify inconsistencies (e.g., resulting from additional electronic validation checks or medical and manual reviews). Resolutions of queries will be made by the investigator or the trial site's designated persons. The query is to be answered directly in the electronic CRF system and the original value will be changed, if necessary.

Coding

Medication names will be coded using the WHO Drug Dictionary (WHO-DD). Medical history terms and adverse events will be coded using the Medical Dictionary for Regulatory Activities (MedDRA). As required by the sponsor's standard operating procedures (SOPs), the versions most recently implemented by the sponsor will be used at the time of database lock. Coding will be reviewed by the sponsor's personnel according to standard procedures.

External data

Trial data not recorded in the CRF (e.g., safety laboratory data, ECG data, and e-diary data) will be reconciled against CRF data (details of reconciliation will be specified separately but may include trial number, trial site number, subject number, age, dates of visits). All external data will be transferred electronically to the data management center using a secure method at predefined intervals during the trial in a data structure defined by the data management center. At the end of the trial, the contract research organization(s) providing these data will provide the data management center with a complete and clean data transfer.

Database lock

When all data have been received and entered into the trial database, all data checks and quality control checks have been performed, all queries are resolved, and the final statistical review has been held without resulting in new queries, the trial database will be considered clean and the data will be locked. For the main analysis (Part 1 and the first 12 weeks of Part 2), the detailed procedure will be described in the data management plan.

13.4 Source data

Source data is defined by GCP as "all information in original records and certified copies of original records of clinical findings, observations, or other activities in a clinical trial necessary for the reconstruction and evaluation of the trial. Source data are contained in source documents (original records or certified copies)".

Source data comprise clinical documentation, data, and records (e.g., clinic/hospital records, clinical and office charts, laboratory notes, memoranda, subjects' diaries or evaluation checklists, pharmacy

Confidential

Protocol KF5503-66
including Amendment 05Page 86 of 137
DMS version 9.0
27 Jul 2017

dispensing records, recorded data from automated instruments, and data and records arising from departments such as the pharmacy, laboratory, and medico-technical departments) that describe or record the methods, conduct, or results of the trial, the factors affecting the trial, and the actions taken.

All clinical documentation and data arising from the trial will be kept by the investigator, who has to provide direct access for trial-related monitoring, audits, IEC/IRB review, and regulatory inspection.

All data captured in the CRF need to be justified by relevant source data. In certain circumstances, data may only be recorded in the trial-specific CRF and not in other documents. If this occurs, the CRF is considered to be the source document. Data expected to be only recorded in the CRF are: race/ethnic group.

The nature and location of all source data/clinical documentation will be identified and documented by the investigator to ensure that all sources of original data required to complete the CRF are known to the sponsor and/or trial site personnel and are accessible for verification during trial-related monitoring, audits, relevant IEC/IRB review, and inspection(s).

For subject reported outcomes captured directly via a diary, source data is defined as the data residing in the vendor's database.

During trial conduct, the vendor is responsible for data security.

All data captured from all subjects will be sent to the sponsor in human readable form on a read-only compact disc for filing/archiving according to sponsor SOPs.

The investigator will receive all data captured for his or her subjects, in a human readable form, on a read-only compact disc for his or her files after trial completion and finalization of data collection.

13.5 Investigator's site file and the trial master file

The investigator is responsible for the timely filing of all essential documents in an investigator's site file and the sponsor is responsible for the timely filing of all essential documents in the trial master file. As applicable, these files must be available at monitoring visits and during audits or regulatory inspections.

After trial completion, the investigator will ensure that all source data/documentation arising from the trial is recorded, handled, and stored in a way that allows its accurate reporting, interpretation and verification. The investigator will take measures to prevent accidental or premature destruction of these documents.

The investigator will keep the investigator's site file, the source data/documentation arising from the trial according to the prescribed record retention period in the country and/or according to the hospital policy, but at least until informed by the sponsor that the trial-related records are no longer required.

Confidential

Protocol KF5503-66
including Amendment 05Page 87 of 137
DMS version 9.0
27 Jul 2017

14 STATISTICAL METHODS AND SAMPLE SIZE DETERMINATION

The statistical planning and analysis of the trial will be performed by sponsor personnel or by authorized sponsor delegates.

14.1 Sample size rationale

The sample size was estimated to reject the null hypothesis of the inferiority of tapentadol PR to morphine PR when comparing responders evaluated at the end of the 14-day Treatment Period (Part 1, i.e., the primary endpoint). The percentage of responders in both treatment groups is estimated to be 80% based on data from previous trials and extrapolation to the trial population under investigation. The non-inferiority margin is set to a difference of 20% for the primary endpoint.

To show the non-inferiority of tapentadol PR compared to morphine PR using a Farrington-Manning (1990) test by a non-inferiority margin of 20% with at least 80% power and a 1-sided significance level of alpha = 0.1, 69 subjects are required in the FAS, assuming a 2:1 randomization of tapentadol PR:morphine PR.

A one-sided alpha of 0.1 is considered appropriate based on a method proposed by Hlavin et al. (2016). The approach makes use of prior knowledge and the concept of extrapolation from a larger population to a small target population (i.e., pediatric population), to reduce the burden of evidence in pediatrics by relaxing the Type I error, while controlling a certain posterior belief, i.e., confidence after successful pediatric trials, in effectiveness of the drug in children.

Further details for the application of the concept of Hlavin et al. (2016) in the context of this trial are provided in a separate document that is available upon request.

The reviews of the safety data during the trial by the DMC (Section 5.4) have no impact on the sample size.

14.2 Analysis of the trial – statistical analysis

The statistical analysis of this trial will be performed as described and as summarized here in the protocol and given in detail in the SAP.

The statistical analysis of this trial will be planned, performed, and reported by sponsor personnel or by authorized sponsor delegates, in accordance with sponsor SOPs.

Main analysis of the trial

The main analysis of the trial will be performed after all subjects have completed the first 12 weeks (Visit TP3 or Visit OP3) of Part 2.

14.2.1 Analysis populations (analysis sets)

Enrolled population

The Enrolled Set includes all subjects with a signed (by subject, parent(s) or legal guardian(s) as appropriate) informed consent form and if required by local law an assent form.

Allocated Set

The Allocated Set includes all subjects who are allocated to treatment.

Safety Set

The Safety Set comprises all treated subjects, i.e., all subjects in whom IMP was administered (at least once).

Full Analysis Set

The FAS comprises all allocated and treated subjects, i.e., all allocated subjects who were administered any amount of IMP.

Per Protocol Set

The Per Protocol Set defines a subset of the subjects in the FAS without any major protocol deviation affecting the primary endpoint. The Per Protocol Set is only relevant for analyses during Part 1. No protocol deviation during Part 2 leads to exclusion from the Per Protocol Set.

Further details of the Per Protocol Set definitions will be specified in the SAP.

Pharmacokinetic Analysis Set

All subjects who have quantifiable serum concentrations during the Treatment Period will be included in the descriptive pharmacokinetic analysis.

Data from subjects who vomit within 6 hours of administration of IMP during the Treatment Period will be carefully assessed to decide if the data should be included in the pharmacokinetic analysis.

Subgroups

The primary endpoint will also be analyzed according to predefined age group and underlying pain condition. Further details, and also further subgroups, will be specified in the SAP.

14.2.2 General descriptive and graphical methods

Analyses will be performed within the specified subject populations as described in Section 14.2.1.

Separate analyses will be performed for Part 1 and Part 2. The analysis for Part 1 will take into consideration the Treatment Period of Part 1. The analysis for Part 2 will take into consideration the Tapentadol Period and Observation Period of Part 2.

Part 1

For the Treatment Period, baseline measurements are defined as the last evaluation performed before starting IMP (i.e., Visit V1, Visit V2, or an unscheduled visit). For pain assessments, the baseline pain is defined as “pain right now” at Visit V2, and will be assessed before any painful or unpleasant procedure, and before the first intake of IMP.

Part 2

For the Tapentadol Period, baseline measurements are defined as the last evaluation performed before or at Visit VE.

For the Observation Period, baseline measurements are defined as the last evaluation performed before or at:

- Visit VE for subjects entering the Observation Period directly after Part 1.

Confidential

Protocol KF5503-66
including Amendment 05

Page 89 of 137
DMS version 9.0
27 Jul 2017

- Visit ET for subjects switching from the Tapentadol Period to the Observation Period.

General

For continuous variables, descriptive statistics will include number of observations, arithmetic mean, standard deviation, minimum, first quartile (Q1), median, third quartile (Q3), and maximum. For categorical variables, frequency counts and percentages will be used to summarize the results. If applicable, changes from the baseline or predefined time points will be presented descriptively.

Data will also be listed and summarized using graphical displays, as appropriate.

Further analyses are outlined below.

14.2.3 Analysis of subject characteristics data

Subject characteristics data will be analyzed for the Safety Set as described in Section 14.2.2.

14.2.4 Analysis of subject disposition

Subject disposition data will be analyzed for the Safety Set as described in Section 14.2.2.

14.2.5 Analysis of pharmacokinetic data

As described in Section 14.2.2, descriptive statistics and graphical displays will be used to summarize the tapentadol and tapentadol-O-glucuronide serum concentration time data for each time interval specified during the Treatment Period for subjects in the pharmacokinetic analysis set.

The tapentadol and tapentadol-O-glucuronide data will also be subject to a population pharmacokinetic analysis described in a separate analysis plan (see Section 14.3).

14.2.6 Analysis of efficacy data

Unless otherwise stated, efficacy analyses will be performed on the FAS.

14.2.6.1 Primary endpoint (proportion of subjects classified as responders in Part 1)

The analysis of the primary endpoint will be performed on the data collected during the Treatment Period (Part 1). The FAS will be the primary analysis set and the Per Protocol Set will be used as a sensitivity analysis set.

Hypotheses

Null hypothesis: $H_0: p_T - p_C \leq -\delta$

“Treatment with tapentadol” is inferior to “treatment with morphine”.

Alternative hypothesis: $H_A: p_T - p_C > -\delta$

“Treatment with tapentadol” is non-inferior to “treatment with morphine”.

T = treatment with tapentadol; C = treatment with morphine; δ = non-inferiority margin; p_i = responder rate in investigational treatment (T) or active control (C).

As this endpoint is a binomial event rate, it will be summarized by descriptive statistics grouped by treatment group. The standard maximum likelihood estimators for the proportion of subjects classified as responders in each group will be the estimated proportions adjusted for the baseline

Confidential

Protocol KF5503-66
including Amendment 05

Page 90 of 137
DMS version 9.0
27 Jul 2017

pain intensity, age group, and underlying pain condition. To obtain these estimators, a logistic regression model will be fitted to the response using the baseline pain intensity, age group, treatment, and underlying pain condition as explanatory variables. The Farrington-Manning (1990) test will then be applied and an 80% confidence interval calculated. The non-inferiority of tapentadol PR compared to morphine PR will be established if the lower limit of this 2-sided 80% confidence interval of the difference in the above estimated proportions is above the non-inferiority margin of -20%.

A sensitivity analysis will be carried out by fitting a Bayesian logistic regression model to compare the proportion of responders under tapentadol PR and morphine PR. Odds ratios will be calculated. Treatment response is the dependent variable and treatment group, age group at baseline (ageg), underlying pain condition (cancer/non-cancer-related pain), age group x baseline VAS, and age group x baseline FPS-R are possible (but not limited to) explanatory variables. The age group refers to a variable indicating whether, on the basis of the subject's age, to use the VAS pain assessment (for subjects aged 12 years to less than 18 years) in the model, or to use the FPS-R score (for subjects aged 6 years to less than 12 years).

Specifically, if X_i is the response indicator for subject i , then we will assume:

$$X_i \sim \text{Bernoulli}(\lambda_i)$$

$$\log(\lambda_i / (1 - \lambda_i)) = \beta_0 + \beta_1 \text{ageg}_i + \beta_2 \text{cancer}_i + \beta_3 (\text{ageg} * \text{baseline VAS}) + \beta_4 (1 - \text{ageg}) * \text{baseline FPS-R} + \beta_5 \text{treatment}_i + \varepsilon_i$$

Non-informative flat normal priors with zero mean and variance equal to 1000 will be assigned to the regression coefficients β_1 to β_4 . The prior for the treatment effect β_5 (on the log-odds scale) will be a normal distribution with mean = 0.10 and standard deviation = 0.48; this prior distribution has been derived from the [REDACTED] trial (in subjects with moderate to severe chronic malignant tumor-related pain) using a down-weighting factor $a = 0.4$. The prior for the subject-specific random effects ε_i will be normal $(0, \sigma^2)$. A non-informative Gamma $(0.001, 0.001)$ prior will be assigned to the precision of the random effects $1/\sigma^2$.

The posterior distribution for the regression coefficients will not have an analytically closed form. Therefore, Markov chain Monte-Carlo methods will be used to obtain a sample from the posterior distribution for the difference between the response rates in tapentadol PR and morphine PR groups. This sample will be summarized by means of the posterior mean, median, standard deviation and 80% credibility interval. If the lower limit of the 80% credibility interval for the difference of the 2 response rates is >-0.2 , then this would support non-inferiority by this sensitivity analysis.

Further sensitivity analyses are planned (but not limited to), e.g., keeping the criteria for response unchanged except for classifying subjects who stop treatment earlier than 14 days because of no further need for opioid treatment as responders rather than non-responders.

More details on the sensitivity analyses and strategies for handling missing data and discontinued subjects will be described in the SAP.

Confidential

Protocol KF5503-66
including Amendment 05Page 91 of 137
DMS version 9.0
27 Jul 2017

14.2.6.2 Pain scale assessed using a VAS and FPS-R

Descriptive statistics will be provided to evaluate the daily average pain (Part 1) or pain at each visit during the Tapentadol Period (Part 2) as well as changes to baseline for the different trial periods and respective treatment groups, as described in Section [14.2.2](#).

14.2.6.3 Rescue medication

The descriptive analyses of the use of rescue medication during the Treatment Period will focus on mean number of daily doses and the mean total daily dose (mg/kg). The morphine equivalent dose of tapentadol will be calculated so that a comparison of rescue medication with respect to the amount of IMP taken can be made. Comparisons will be made across time and also for subgroups of different ages.

14.2.6.4 Time to discontinuation

A survival analysis of the time to discontinuation of IMP overall, due to lack of efficacy, and due to TEAE will be performed for tapentadol PR and morphine PR for Part 1 (Treatment Period) and for tapentadol PR during the Tapentadol Period of Part 2 if at least 10% of the subjects per group discontinue.

14.2.7 Analysis of safety data

The analysis of safety data will be performed on the Safety Set.

Unless otherwise specified, separate analyses will be performed for the different trial periods and respective treatment groups.

14.2.7.1 Adverse events

The original terms used in the CRFs by investigators to identify adverse events will be coded using the most recent version of Medical Dictionary for Regulatory Activities (MedDRA) implemented by the sponsor.

Adverse events will be categorized by seriousness, intensity, outcome, countermeasures, and relationship to IMP and will be tabulated by system organ class and preferred term. Adverse events will be tabulated separately for the treatment periods.

Those TEAEs which started in Treatment Period and are carried over into Tapentadol Period will be considered as ongoing TEAEs. A worsening of a TEAE in Tapentadol Period in a subject previously treated with morphine PR in Treatment Period will be considered as a new TEAE.

The frequency and severity of adverse events will be analyzed descriptively as described in Section [14.2.2](#) both on a subject and event-based level.

All adverse events will be listed. Serious adverse events will be listed separately. Non-TEAEs will be listed separately.

Special attention will be given to those subjects who have discontinued treatment due to an adverse event or who experienced a severe or a serious adverse event. Such cases will be analyzed individually.

Confidential

Protocol KF5503-66
including Amendment 05Page 92 of 137
DMS version 9.0
27 Jul 2017

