15.1 Secondary endpoint

The main secondary endpoints are:

Part 1

Constipation as assessed by changes from baseline of total scores for the modified constipation assessment scale (mCAS).

Part 1 and Part 2

Tolerability as assessed by the number and type of adverse events and adverse drug reactions by treatment arm during the different trial periods, on a subject and event level.

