15.1.2.1 Analyses of adverse events

The following overview tables of TEAEs will be generated as described in Section [8.1](#) for Part 1 and the Tapentadol Period of Part 2. For Part 1, in addition to the presentation by treatment arm, descriptive summaries will also be presented overall.

1. Summary of the number and percentage of subjects with at least one:

- TEAE.
- Serious TEAE.
- Non-serious TEAE.
- Unexpected TEAE.
- Related TEAE.
- Related serious TEAE.
- TEAE leading to discontinuation from IMP.
- TEAE leading to discontinuation from the trial.
- Deaths.

For Part 1 in addition:

- TEAE of Part 1, that are ongoing during the Tapentadol Period of Part 2.
- TEAE of Part 1, that are ongoing during the Observation Period of Part 2.
- TEAE of Part 1, that actually started during the Observation Period of Part 2 (within the therapeutic reach of the last IMP intake of the Treatment Period).

For Tapentadol Period of Part 2 in addition:

- TEAE of Part 1, that are ongoing during the Tapentadol Period of Part 2
- TEAE of Tapentadol Period of Part 2, that actually started during the Observation Period of Part 2 (within the therapeutic reach of the last IMP intake of the Tapentadol Period)
- TEAE of Tapentadol Period of Part 2, that are ongoing during the Observation Period of Part 2

2. Summary presenting the number of TEAEs per subject categorized as 0, 1, 2, 3, 4, 5, and >5.
3. Summary of the number and percentage of TEAEs for:
 - TEAEs.
 - Serious TEAEs.
 - Non-serious TEAEs.
 - Unexpected TEAE.
 - Related TEAEs.
 - Related serious TEAEs.
 - TEAE leading to discontinuation from IMP.
 - TEAE leading to discontinuation from the trial.

For Part 1 in addition:

- TEAE of Part 1, that are ongoing during the Tapentadol Period of Part 2.
- TEAE of Part 1, that are ongoing during the Observation Period of Part 2.
- TEAE of Part 1, that actually started during the Observation Period of Part 2.

For Tapentadol Period of Part 2 in addition:

- TEAE of Part 1, that are ongoing during the Tapentadol Period of Part 2.

- TEAE of Tapentadol Period of Part 2, that actually started during the Observation Period of Part 2.
- TEAE of Tapentadol Period of Part 2, that are ongoing during the Observation Period of Part 2.

The percentage denominator will be the total number of TEAEs.

In addition, these overview tables will be presented for subgroups as specified in [Table 4](#).

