- Pre-treatment (Part 1 only, all enrolled subjects, by treatment arm and overall)
 - Non-TEAE.
 - Serious non-TEAE.
- Post-treatment (all trial Periods together, SAF, presenting the arms of the Observation Period)
 - Non-TEAE.
 - Serious non-TEAE.

Percentages will be calculated related to the total number of subjects/events presented in the respective table as outlined above for the TEAE tables by SOC and PT.

Analysis by System Organ Class, Preferred Term and descriptors

For Part 1 and the Tapentadol Period of Part 2, the number and percentage of events will be summarized by SOC and PT (sorted alphabetically) for the following AE descriptors. Presentations will be for TEAEs only.

- Intensity: mild, moderate, severe.
- Causal relationship to the IMP: related (with subcategories: possible, probable/likely, certain), not related (with subcategories: not related, unlikely), unknown (with subcategories: conditional/unclassified, assessable/unclassifiable, causal relationship missing).
- Outcome: recovered/resolved, recovering/resolving, not recovered/not resolved, recovered/resolved with sequelae, fatal, unknown.
- Non IMP related countermeasures: none, newly started medication, trial discontinuation, others.
- Action taken with IMP: dose increased, dose reduced, drug interrupted, drug withdrawn, dose not changed, not applicable, unknown.
- Measures of location and variation will be calculated for:
- Duration of TEAEs: Duration will be analyzed in days with measures of dispersion and variation.
- Time to onset of TEAE will be analyzed in days with measures of dispersion and variation.

Denominator for percentage calculation will be the number of all TEAEs for presentation over all SOCs, and the number of TEAEs per SOC or PT respectively for the presentation per SOC and PT, respectively.

The number and percentage of all post-treatment non-TEAEs (all Periods together) will be summarized by SOC and PT (sorted alphabetically) for the following AE descriptors:

- Intensity.
- Time to onset of post-treatment non-TEAEs after last IMP administration will be summarized with measures of dispersion and variation.

Listings

The following listings will be produced for all enrolled subjects:

- Deaths.
- Serious adverse events other than death.
- AEs leading to discontinuation from the trial.
- AEs leading to discontinuation from IMP.
- AEs leading to IMP dose decrease or interruption of IMP.

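### The protocol promises adverse-event severity by subject and by event, but the SAP tabulates intensity by event only, so no planned table gives the share of children with a severe TEAE

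*Protocol*

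**What the plan says.** Protocol 14.2.7.1 makes three relevant commitments. On measure and level: "The frequency and severity of adverse events will be analyzed descriptively", and this "both on a subject and event-based level". On documentation: "All adverse events will be listed". On notable cases, it gives special attention to subjects who stopped treatment because of an adverse event or "who experienced a severe or a serious adverse event. Such cases will be analyzed individually".

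SAP 15.1 repeats that tolerability is assessed "during the different trial periods, on a subject and event level".

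Intensity (mild, moderate, severe) is tabulated in one part of the SAP, the descriptor analysis in 15.1.2.2. There, "the number and percentage of events will be summarized by SOC and PT (sorted alphabetically) for the following AE descriptors", and "Denominator for percentage calculation will be the number of all TEAEs for presentation over all SOCs"; within a System Organ Class (SOC) or Preferred Term (PT), the denominator is the number of TEAEs in that class or term. Post-treatment events that are not treatment-emergent also have intensity summarised by event.

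The subject-level overview in SAP 15.1.2.1 opens "Summary of the number and percentage of subjects with at least one" and then names its rows. None concerns intensity. SAP 7.1 records no departure from the protocol's analysis.

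**The concern.** Severe and serious are different attributes in this protocol. Section 12.6.1 defines severe by interference with usual daily activity, and serious by outcomes such as death, threat to life or hospitalisation. A child can have a severe event that is not serious and does not lead to stopping or changing treatment. That child is counted in the subject overview as having a TEAE, but nothing there shows that the event was severe. Protocol 6.2 names nausea, dizziness, somnolence, headache and constipation as the most common reactions to tapentadol PR, and these can be severe without being serious.

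The usual question when comparing two opioids is what proportion of children in each arm had at least one severe event. Anyone following the SAP exactly would not produce that proportion. A reader who turns to the event table instead would see a percentage whose denominator depends on how many milder events each arm reported.

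**Working it through.** **Step 1: compare the promise with each planned output.** Protocol 14.2.7.1 requires severity at subject level and at event level. The SAP's adverse-event outputs are:

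| SAP output | Unit | Intensity shown? |
|---|---|---|
| 15.1.2.1, summary 1 (any, serious, non-serious, unexpected, related, related serious, leading to discontinuation of treatment or trial, deaths, carry-over rows) | Subjects | No |
| 15.1.2.1, summary 2 (number of TEAEs per subject, 0 to >5) | Subjects | No |
| 15.1.2.1, summary 3 | Events | No |
| 15.1.2.2, incidence by PT and by SOC/PT (all, serious with related and fatal subsets, non-serious, related; non-TEAEs before and after treatment) | Subjects and events | No |
| 15.1.2.2, descriptors | Events | Yes |
| 15.1.2.2, named listings (deaths, other serious events, events leading to discontinuation, dose decrease or interruption, events starting on the day of Visit VE) | Cases | No listing of severe events |
| 15.1.2.3, exposure-adjusted rates | Subjects per year | No |

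SAP 18.1.11.4 keeps the highest intensity when consecutive episodes of one adverse event in one subject and period are merged. That rule works within a single event. It does not give a worst intensity per subject.

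The event-level half of the severity commitment is met. The subject-level half is not.

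**Step 2: ask whether the event table can substitute.** The documents state no figure on this point, so there is none to reproduce. Inputs: 69 subjects allocated 2:1 (SAP 5.2), which gives 69 × 2/3 = 46 on tapentadol and 69 × 1/3 = 23 on morphine. All event counts below are assumptions for illustration.

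- Subject-level share = children with at least one severe TEAE ÷ children in the arm.
- Event-level share = severe TEAEs ÷ all TEAEs in the arm.

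| Case | Arm | Subject level | Event level |
|---|---|---|---|
| A: equal shares of children | Tapentadol | 6/46 = 13.0% | 6/60 = 10.0% |
| | Morphine | 3/23 = 13.0% | 3/60 = 5.0% |
| B: ranking reversed | Tapentadol | 4/46 = 8.7% | 4/40 = 10.0% |
| | Morphine | 4/23 = 17.4% | 4/80 = 5.0% |
| C: one event share, two subject shares | Tapentadol, one child has all six severe events | 1/46 = 2.2% | 6/60 = 10.0% |
| | Tapentadol, six children have one each | 6/46 = 13.0% | 6/60 = 10.0% |

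The gap can also run the other way. With 10/46 = 21.7% and 5/23 = 21.7% of children affected, once each, and an assumed 4 and 2 TEAEs per child, the event shares are 10/(46 × 4) = 10/184 = 5.4% and 5/(23 × 2) = 5/46 = 10.9%.

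**Step 3: what the event count adds.** The SAP gives the number of severe events as well as the percentage. Each affected child contributes at least one severe event, so the count is an upper bound on affected children: 6 in both lines of case C. It does not separate 1 child from 6.

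**The case against.** The strongest reply is that most of the information is already in the planned output. The table shows severe-event counts, which cap the number of affected children. Summary 2 and the SOC/PT tables show how many events each arm reported, so a reader could see why denominators differ. The protocol requires a full listing and individual analysis of severe cases, and the SAP, which names particular listings, does not withdraw the full one. SAP 15 plans no statistical test on safety data. All of this stands, and it limits the point. It does not close the gap: a cap, a listing and case reviews are not the descriptive subject-level analysis that the protocol commits to.

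Three stronger readings are tempting, and the documents do not support them.

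- A reader might infer that children with severe events go unreported. They do not, because the full listing and the case reviews identify them. What is missing is the summary per arm.
- A reader might infer that a main secondary endpoint is left unanalysed. That endpoint (Protocol 8.1.2, SAP 15.1) is tolerability by number and type of adverse events and adverse drug reactions. Intensity is not part of the definition, and number and type are covered at both levels. The severity commitment comes from Protocol 14.2.7.1 alone.
- A reader might infer that the planned table will distort the comparison two-fold. That contrast comes entirely from the assumed event counts; nothing in the documents predicts such an imbalance.

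**Conclusion.** The point holds as an undeclared mismatch between protocol and SAP, specific to intensity. Seriousness, relatedness and discontinuation are all given per subject; severity is not. Following the SAP exactly yields no number or percentage of children per arm with a severe TEAE, and the event percentage is not a substitute.

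The size is modest. Sample size, alpha, margin and the primary analysis are untouched, and no inference rests on the event percentage. The numerical examples show what could be misread, not what is expected. The conclusion rests on the SAP text as written. The table shells mentioned in SAP 18.3 are a separate document that was not available; even if they contain such a row, the SAP does not call for it.

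**What to change.** In SAP 15.1.2.1, summary 1, add a row for severe TEAE: number and percentage of subjects with at least one, with all Safety Set subjects in the arm as denominator (for the Tapentadol Period, those who entered it). Apply it to Part 1 and to the Tapentadol Period, and keep the event-level intensity table of 15.1.2.2.

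A table of subjects by worst intensity and a listing of severe TEAEs are optional additions; with about 46 and 23 children, a split by SOC and PT would be sparse. A severe row in summary 3 is unnecessary, because the descriptor table already gives intensity over all SOCs with all TEAEs as denominator.

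The cost is a line of SAP text and one table row per period, repeated in the subgroup versions of the overview that the SAP already plans. Intensity is collected for every adverse event (Protocol 12.6.1), so no new data are needed. If the sponsor prefers not to add the row, SAP 7.1 should declare the departure from Protocol 14.2.7.1.
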